NCT05604014

Feasibility Study of the My Health Coach App for Adults with Fetal Alcohol Spectrum Disorders (FASD)

Principal Investigators - [name] & [name].

PREFACE

This study represents the third phase of a larger research project developed for a UH2 application through the Collaborative Initiative on Fetal Alcohol Spectrum Disorders (CIFASD), which has been funded by the National Institutes on Alcohol Abuse and Alcoholism since 2003. The project aims to develop a mobile health (mHealth) application (app) for adults with fetal alcohol spectrum disorders (FASD). In the first phase (IRB Study #00004616), we utilized focus groups to engage adults with FASD in the development of the mHealth intervention, currently called "My Health Coach." In our second phase (IRB Study 0007156), we used an online survey to obtain feedback on the developed concept from a broader sample of adults with FASD. In this third phase, we are conducting a feasibility trial of the developed mHealth intervention.

1. PURPOSE OF STUDY

This project is a partnership with identified leaders in the adult FASD community, known as the Adult Leadership Collaborative (ALC). Their motto is: "Nothing About Us Without Us." The purpose of this study is to conduct a feasibility study of the My Health Coach app we have developed from stakeholder feedback in prior phases. We will test both the acceptability and feasibility of the app for adults with FASD as well as trial procedures. These data will inform our future larger-scale randomized controlled trial.

We will recruit adults with FASD online through well-established methods by our research group and our ALC partners. Eligible adults will try out the app on their own smartphones. Online assessments will be completed at the start of the study and six weeks later. Interviews will also be completed to further understand user experiences.

This project has the potential to make significant contributions to the field as there are currently no evidence-based supports for adults with FASD.

2. BACKGROUND AND RATIONALE

Prenatal alcohol exposure affects the developing brain and other organ systems and can result in a set of conditions termed fetal alcohol spectrum disorders (FASD; [1]). FASD are prevalent conditions, affecting about 2 to 5% of the North American population [2]. Although FASD have been primarily studied in children, it is well established that FASD are life-long conditions that impact multiple domains functioning. Adults with FASD often require a higher level of supports to participate in home, community, occupational, and social settings [3].

Despite the high prevalence, most people with FASD do not receive appropriate diagnosis or services. Research has documented that 80% or more of people with FASD go undiagnosed [4]. Getting an early diagnosis and appropriate services are two important protective factors against mental health symptoms and other later life problems such as school disruptions, trouble with the law, and substance use [3].

Page 1 of 13

Unfortunately, research on effective services for people with FASD is limited, and almost non-existent for adolescents and adults. In addition, there are major barriers to accessing available services and supports in the community. Barriers to care occur because a knowledgeable and skilled workforce is lacking [5-6], and there are individual- and family-level barriers such as limited financial resources, transportation, and stigma [7].

This project will initiate formative research to guide the development of mHealth tools for adults with FASD. Most adults have a smartphone and mHealth apps have the advantage of being easily scalable and can reduce barriers to access. In addition, mHealth apps are well-suited for providing information, self-monitoring, goal-setting, and real-time synchronous communication, all of which can be effective behavior change techniques [8].

Consistent with the Developmental Origin of Health and Disease (DOHaD) hypothesis, emerging research is documenting high rates of co-occurring chronic health conditions associated with prenatal alcohol exposure in humans and animal models [9,10]. In fact, the ALC has been instrumental in directing attention to this important issue and leading a large survey-based study on this topic [11]. Adults with FASD require concrete and accurate information to understand their condition and practical ideas to meet their needs and build on their strengths. Our mHealth app, currently called My Health Coach, will offer adults with FASD evidence-based education about their condition and tools to promote their own self-management and health advocacy goals. My Health Coach is grounded in self-determination theory [12] and integrates well-established behavior change strategies [13]. It uses a just-in-time adaptive intervention design [15] and a simple and engaging chatbot interface. This will provide adults just the right type and amount of support, when they are most receptive.

Partnering with the ALC to develop and conduct the research is an important strength of this study. Gathering key stakeholder input is crucial when developing new treatments and supports for a given condition. But partnering with identified leaders in the community to help shape the research questions and guide data collection and interpretation enriches the quality of the data and ensures the right questions are being asked.

3. ADMINISTRATIVE ORGANIZATION

This study is led by Drs. [name] and [name]. [name] is faculty at Mt. Hope Family Center and has appointments in the departments of Psychology and Pediatrics. [name] is faculty in the department of Electrical and Computer Engineering. They will oversee all research staff, implementation of human subjects' protections, and data collection, management, analysis, and reporting.

All data collection will be through our research team at the University of Rochester. Participants will be recruited online and complete informed consent, screening, and survey through our REDCap database, hosted at the University of Rochester. Interview data will be collected via HIPAA-complaint Zoom. Additional data will be collected through the My Health Coach app developed and managed by our team and hosted on a URMC Amazon Web Services (AWS) account.

4. STUDY DESIGN

Page 2 of 13

This feasibility study will use a single group design with assessment timepoints prior to the receipt of the app and 6-weeks later. Primary outcomes assessed will include quality of life, self-determination theory constructs (i.e., autonomy, competence, relatedness), self-management, and barriers to care. Acceptability of the app and trial procedures will also be assessed at the 6-week timepoint.

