5. SUBJECT POPULATION

The study population will include adults (18+) with FASD. We will aim to enroll 48 adults with FASD to achieve a final sample of 40 participants with complete data. Additional participants will be enrolled if attrition is greater than anticipated.

In prior studies conducted by the ALC, 45% of participants were from Canada, 40% from USA, 9% European countries, 5% Australia / New Zealand, and 2% African countries. As such, we anticipate the vast majority of participants in our study will also be from the US and Canada. However, some will likely come the EU and UK and fall under GDPR requirements. A "Notification for Collection and Use of Personal Data" is included in the REDCap Screening Module immediately after the Study Consent Form to inform all participants from the EU or UK about compliance with GDPR requirements.

It is also possible that some adults with FASD will have legal guardians due to decisional impairment (in either specific or global domains). For these adults to participate, their legal guardian would also need to review the study consent form and provide written permission. Legal guardianship in Canada is rare but is used sometimes for adults with FASD in the US. A question in the screening module asks about legal guardianship. For those adults who indicate they have a legal guardian, our research team will contact that person to go over the permission form and obtain the needed signature through REDCap.

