9. STUDY PROCEDURES

The project research assistant will track participants in REDCap once enrolled and will facilitate timely completion of research assessments. All participants will be encouraged to complete assessments, regardless of their level of engagement with the My Health Coach app. Actual user data from the app (whether minimal or extensive) will be important in addressing study aims.

After informed consent, participants will be asked to complete a set of baseline surveys (see details on the assessment battery below). To be most sensitive, given the unique neurobehavioral profiles of participants, administration will be flexible based on participant needs and can include surveys completed independently online, over the phone or Zoom with research staff, or through the mail. Afterwards, they will be provided information on how to install the app on their phones. Study staff will be available to troubleshoot problems with installation or app use. After 6 weeks, all participants will be re-contacted to complete follow-up surveys. User implementation data will be gathered through the app. To further assess acceptability, satisfaction, and barriers and facilitators of app use, the study research assistant will complete qualitative interviews with participants over HIPAA-complaint Zoom or telephone. Interviews will be recorded and later transcribed verbatim.

Study Assessment Battery

Measure	Baseline	6-Week
		Follow-up
Quality of Life: Personal Well-being Index – Intellectual	X	X
Disability Version		
Self-Determination: The Basic Psychological Need	X	X
Satisfaction and Frustration Scale		
Self-Management	X	X
Barriers to Healthcare Checklist	X	
FASD Education	X	
Basic Demographics	X	
Acceptability: Theoretical Framework of Acceptability		X
measure		

Page 6 of 13

Qualitative Interview on User Experience		X
--	--	---

Qualitative Interview. The semi-structured questioning route will cover the following topics: 1) overall impressions of My Health Coach; 2) experience using the app (both facilitators and barriers of use); and 3) perceived impact on their health and well-being. Interviews are expected to last about 30 minutes.

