17. DATA ANALYSIS PLAN

Pre-Post Intervention Outcomes. Descriptive statistics, reliability indices, and pre-post effect sizes (Cohen's d) will be calculated for baseline and follow-up quantitative measures and user implementation data. Data will provide useful estimates to inform larger randomized control trials of the app. Data will also guide further app refinements.

Qualitative Interviews. Data will be analyzed thematically to understand users' experiences with the My Health Coach app and research trial. The purpose is to inform further app development. Thematic analysis focuses on identifying patterns or themes within the data. Consistent with the approach advocated by Miles, Huberman, and Saldana [15], research team members will first familiarize themselves with the data, iteratively reviewing each transcript, and independently assigning initial codes ("first-level coding"). The team will then come together and discuss, operationalize, and refine each code. We will also generate "second-level codes" which consider categories or deeper meanings among first-level codes. During this process we will examine interrelationships and networks among codes and build a preliminary thematic framework. Transcripts will then be recoded and codes refined through further discussion and consensus, as needed. Participant and group "fit" with the framework will also be assessed, with confirmatory and disconfirmatory evidence for the model examined. Participant matrices may also be utilized to examine variance in themes across participants and key demographic factors, pre-post intervention change, or usage patterns.

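### Barriers to care is listed as a primary outcome, but its only named measure is scheduled at baseline, so no change over 6 weeks can be estimated for it

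*Combined protocol and SAP*

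**What the plan says.** Section 4 sets out a "single group design with assessment timepoints prior to the receipt of the app and 6-weeks later". Its next sentence reads: "Primary outcomes assessed will include quality of life, self-determination theory constructs (i.e., autonomy, competence, relatedness), self-management, and barriers to care".

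The Study Assessment Battery in Section 9 has a baseline column and a 6-week column. The row "Barriers to Healthcare Checklist" carries a mark under baseline and none under 6 weeks. The quality of life, self-determination and self-management rows carry a mark in both columns.

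The 6-week interview, also in Section 9, includes "experience using the app (both facilitators and barriers of use" among its topics. Section 2 uses barriers in another sense, as "major barriers to accessing available services and supports in the community".

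Section 5 aims for a "final sample of 40 participants with complete data" from 48 enrolled. Section 17 plans descriptive statistics, reliability indices and pre-post Cohen's d, and gives the purpose: "Data will provide useful estimates to inform larger randomized control trials of the app".

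**The concern.** An outcome of receiving the app needs at least one value taken after the app is received. For barriers to care the schedule provides none. The two sections cannot both be followed as they stand: Section 4 makes barriers an outcome, while the battery treats the checklist like FASD Education and Basic Demographics, which are also collected once at the start.

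At stake is the change estimate for one stated primary domain. There would be no follow-up mean, no change score and no pre-post effect size to carry into the later randomized trial. Once a participant's 6-week survey has gone out without the checklist, that value cannot be recovered. At reporting, the authors would have to drop a declared primary outcome or present a baseline-only figure as one.

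**Working it through.** The documents give no stated figure to reproduce here. The check sets the outcome list in Section 4 against every row of the Section 9 battery, and then against Section 17.

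**Step 1: the battery, row by row.**

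| Battery row | Baseline | 6 weeks | Primary in Section 4? |
|---|---|---|---|
| Quality of life | X | X | Yes |
| Self-determination (autonomy, competence, relatedness) | X | X | Yes |
| Self-management | X | X | Yes |
| Barriers to Healthcare Checklist | X | – | Yes |
| FASD Education | X | – | No |
| Basic Demographics | X | – | No |
| Acceptability measure | – | X | No |
| Qualitative interview | – | X | No |

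Of 8 rows, 3 are marked at both visits, 3 at baseline only and 2 at 6 weeks only. Of the 4 primary domains, 3 are marked at both visits and 1 is not. Counted as single constructs, this is 1 of 6: quality of life, autonomy, competence, relatedness, self-management, barriers.

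**Step 2: is the empty cell a fault of text extraction?** Unlikely. Rows with two marks keep both, and the two follow-up-only rows keep their empty baseline cell, so column positions survived.

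**Step 3: does anything else at 6 weeks fill the gap?** The interview covers overall impressions, facilitators and barriers of app use, and perceived impact on health and well-being. Section 2 describes barriers to care as workforce gaps, finances, transportation and stigma. Difficulty using an app is a different construct. The perceived-impact topic might draw a relevant remark, but it is qualitative and has no baseline counterpart. The content of the self-management measure is not described, and it is not presented as a measure of barriers to care.

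**Step 4: consequence under Section 17.** A pre-post d needs a baseline and a 6-week value from the same participant. Barriers to care has 0 follow-up values, hence 0 pairs, whatever the number enrolled. Section 17 gives it no separate analysis.

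**Step 5: what the other domains obtain, for scale.** The plan is 40 complete out of 48 enrolled, an implied loss of (48 − 40)/48 = 16.7%; the protocol states no attrition rate. Take d as mean change divided by the SD of change (an assumption, since Section 17 names no standardiser) and set t = d√n. The 95% limits for d are then the noncentrality values δ that place t at the 2.5% and 97.5% points of the noncentral t with n − 1 degrees of freedom, divided by √n. With n = 40, and with values of d that are assumed because the documents give none:

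- d = 0: −0.31 to 0.31
- d = 0.2: −0.11 to 0.51
- d = 0.5: 0.17 to 0.83

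The half-width is about 0.31 at d = 0 and (0.83 − 0.17)/2 = 0.33 at d = 0.5. This is roughly the precision barriers to care would have if the checklist were repeated. As scheduled there is no estimate at all.

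**The case against.** The strongest reply is that little turns on this. Section 1 gives the purpose as acceptability and feasibility, and neither is touched. No test, decision rule or sample size uses barriers to care. The slip may be only one of wording: Section 12 names self-management, advocacy and quality of life as possible benefits and omits barriers, and the app features in Section 9 do not directly address most of the barriers in Section 2. On that reading the checklist was always a baseline descriptor.

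The limit on harm stands. The inference about intent does not settle the matter, because Section 2 also presents mobile apps as a way to lower barriers to access, which fits an outcome. Even if the slip is in Section 4, a primary outcome list that names something the study will not measure after the intervention is wrong as written.

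A second reply is that Section 4 never says each primary outcome is a change score. That is true. But its two-visit design and the pre-post heading in Section 17 make change the natural reading, and a value taken before the app cannot be an outcome of it on any reading.

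Three narrower points stand:

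- Forty is the target for complete data, not a ceiling on pairs; 48 are to be enrolled, and more if attrition is high.
- The intervals above give scale only. The defect does not depend on them.
- The documents do not say whether follow-up is still under way, so the remedy must be conditional.

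**Conclusion.** The concern holds. Sections 4 and 9 conflict on a primary outcome, and nothing elsewhere resolves the conflict. Of four primary domains, three are planned to have 40 pairs each and barriers to care has none, so Section 17 can give no pre-post effect size for it. Baseline descriptives and reliability for the checklist remain available and can still inform the later trial.

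The conclusion rests on the battery table being complete and on its column marks being read correctly; the pattern of the other rows supports both. It needs no assumption about effect size, attrition or standardiser. The documents do not show which section reflects the intent. The conflict should be resolved because it concerns the primary outcome list and because each missed 6-week value is lost for good.

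**What to change.** The investigators should state which section was intended and amend the other.

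1. **If barriers to care is an outcome:** mark the Barriers to Healthcare Checklist at the 6-week follow-up in the Section 9 battery, before further 6-week surveys are sent. The instrument and the survey already exist. The cost is extra participant burden, whose size the documents do not state. Participants already past 6 weeks would have no pair, and their number should be reported.
2. **If it describes the sample:** remove it from the primary outcomes in Section 4 and list it as a baseline characteristic. This is a short edit. The cost is that the study then gives no change estimate for barriers to care.

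If follow-up is already complete, only the second route is open, and the change to the outcome list should be disclosed in the report.

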5. SUBJECT POPULATION

The study population will include adults (18+) with FASD. We will aim to enroll 48 adults with FASD to achieve a final sample of 40 participants with complete data. Additional participants will be enrolled if attrition is greater than anticipated.

In prior studies conducted by the ALC, 45% of participants were from Canada, 40% from USA, 9% European countries, 5% Australia / New Zealand, and 2% African countries. As such, we anticipate the vast majority of participants in our study will also be from the US and Canada. However, some will likely come the EU and UK and fall under GDPR requirements. A "Notification for Collection and Use of Personal Data" is included in the REDCap Screening Module immediately after the Study Consent Form to inform all participants from the EU or UK about compliance with GDPR requirements.

It is also possible that some adults with FASD will have legal guardians due to decisional impairment (in either specific or global domains). For these adults to participate, their legal guardian would also need to review the study consent form and provide written permission. Legal guardianship in Canada is rare but is used sometimes for adults with FASD in the US. A question in the screening module asks about legal guardianship. For those adults who indicate they have a legal guardian, our research team will contact that person to go over the permission form and obtain the needed signature through REDCap.

6. INCLUSION AND EXCLUSION CRITERIA

- Adult 18 years or older
- Have a history of prenatal alcohol exposure or FASD diagnosis (based on self-report)
- Have fluency in English
- Own an Android or iOS (iphone) smartphone
- For adults with a legal guardian: their parent or guardian needs to provide written permission for them to participate

Participants who are not able to speak English will be excluded from the study at this time as the My Health Coach app and surveys are only currently available in English.

7. RECRUITMENT METHODS

We will use well-established recruitment methods previously used by our University of Rochester research group and ALC partners. Recruitment materials include study flyers and social media tiles (see uploaded). These materials will be distributed as follows:

- [name] will share study recruitment materials with providers and community advocates who regularly interact with adults with FASD
- We will post study information on our team's Twitter account (@FMFConnect) and newsletter (www.fmfconnect.com)

Page 3 of 13

- CIFASD investigators can inform research participants or patients in their local sites or clinics for which they have routine access
- FASD United (Formerly National Organization on Fetal Alcohol Syndrome) is a member of CIFASD and has a mission to educate the public about FASD and disseminate research and policy information. They can disseminate the study flyer through their Weekly Round-Up newsletter, significant social media presence, and to their state and local affiliates who can share in their communities
- ALC partners will share recruitment materials through their social media and other networks
- Organizers/moderators of popular social media groups can be sent recruitment materials and can choose to share with their members

We would also like to invite participants to consider participating in the current study who completed informed consent and screening for our prior focus group study (IRB Study #00004616) or online survey (IRB Study 0007156). These adults would be sent an email (see email language template) including the study recruitment flyer. Interested participants from prior studies would need to follow the same consenting and data collection procedures outlined below as other new participants. Recruitment materials would direct them to the REDCap Screening Module.

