for "live in UK or EU"), or to send them surveys or schedule interviews. This contact information would also allow us to remove or change participant data as requested by a participant under GDPR requirements if needed. Identifying information will be stored separately from other de-identified data sources. In addition, this study is minimal risk and involves procedures (e.g., survey responses, app usage) for which written consent is not normally required outside the research context. There is also not an easy way to verify participant identify for written eConsent without creating an additional step for participants involving communication with research staff through another method (e.g., email, phone).

After reviewing the information sheet, participants will be directed in REDCap to answer screening questions to assess eligibility for the study (see Screening Form). If eligibility criteria clearly aren't met (e.g., out of age range, no smartphone, etc), participants will be informed immediately that they aren't eligible and the module will end. Screening data will be maintained for ineligible participants to aid in clinical trial reporting requirements (e.g., documenting numbers screening, eligible vs. ineligible, and reasons).

For adults who appear to meet criteria or in cases where they answer "unsure" for any of the questions, further contact information will be gathered. Contact information will also include necessary variables to generate their "globally unique identifier" (GUID), which is used in other CIFASD studies and required for the NIAAA-Data Archive (https://nda.nih.gov/s/guid/nda-guid.html).

Legal Guardians: For legal guardians, written permission will be obtained using REDCap's eConsent signature field. A study team member will contact the legal guardian based on information provided by the participant in their survey. During this contact the study team will provide the legal guardian a passcode to enter when completing the eConsent to serve as verification of their identity. The legal guardian will then select "Next Page" and a read only copy of the consent will be generated that they can review, download, and/or print. At the bottom of the page, they will need to select "I certify that all the information in the document above is correct, and I understand that signing this form electronically is the equivalent of signing a physical document." Once this is selected, they will be able to submit the signed consent form.

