16. PRIVACY AND CONFIDENTIALITY OF SUBJECTS AND RESEARCH DATA

All data will be used solely for research purposes and will be securely locked in designated file cabinets, URMC managed Box folder dedicated to project, Project REDCap database, and an encrypted, HIPAA-complaint Cloud database (AWS; for data collected via the app; see above). Identifying information will be stored separately from other data, which will be stored by research ID number (GUID). Multiple procedures will be implemented to protect participant data collected through the app, which are further detailed in the section "Protections Against Risks" and Data Security Assessment form. Only senior key personnel and project research staff will have access to the data.

The following table summarizes the project data flow. MHFC IT will set up and manage permissions for URMC Project Box folder. Only project staff will have access to REDCap and Box folders. [name] will coordinate with the CIFASD5 Coordinating Center to facilitate required data uploads to NIAAA-Data Archive as required by the grant for eligible de-identified data (pre-post surveys; all other data exempt).

Data Element	How Data	Where Data is	How Data is Managed
	Collected	Stored	
Information	REDCap	REDCap, Back-ups	MHFC IT; Project Staff
Sheet,		URMC Box	
Screening			
Survey,			
Contact			
Information			
Legal Guardian	REDCap	REDCap, Research	MHFC IT; Project Staff
Permission		staff signed copy of	
Form		permission form on	
(eConsent)		URMC Box	
Baseline (T1)	REDCap	REDCap, Back-ups	MHFC IT; Project Staff;
Surveys		URMC Box,	CIFASD5 Coordinating
		CIFASD/NIAAA-DA	Center
6-week	REDCap	REDCap, Back-ups	MHFC IT; Project Staff;

Page 9 of 13

Follow-up (T2)		URMC Box,	CIFASD5 Coordinating
Surveys		CIFASD/NIAAA-DA	Center
Follow-up	Zoom, back-	URMC Box	MHFC IT; Project Staff;
Interview	up audio		Audio/video data is
	recording		transcribed verbatim;
			audio/videos deleted once
			transcript verified
My Health	User device	URMC-managed	Access is restricted to
Coach App	synchronized	account on AWS	authorized individuals and
usage data and	with AWS		every access to the data will
User's inserted			be logged, data is encrypted
data			in transit and at rest. AWS
			account is set up in
			compliance with UR/URMC
			policies and monitored by
			Lacework.

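### Does the plan need to report how many enrollees had been involved in the earlier phases that shaped the app?

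*Combined protocol and SAP*

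**What the plan says.** The Preface places this study third in a sequence. In the first phase, "we utilized focus groups to engage adults with FASD in the development of the mHealth intervention"; in the second, "we used an online survey to obtain feedback on the developed concept from a broader sample of adults with FASD". Section 7 then lists the recruitment channels and adds that the team would like to invite "participants to consider participating in the current study who completed informed consent and screening for our prior focus group study", or for the survey. They are emailed the flyer and follow the same consent and data-collection steps as anyone else.

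Section 1 gives the aim: "We will test both the acceptability and feasibility of the app for adults with FASD as well as trial procedures". It continues: "These data will inform our future larger-scale randomized controlled trial". Section 5 sets the size: "We will aim to enroll 48 adults with FASD to achieve a final sample of 40 participants with complete data".

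Section 17 plans descriptive summaries, reliability figures and Cohen's d for pre-post change, together with app-usage data and a thematic analysis of interviews. It does not mention earlier involvement. Section 8 says screening data on ineligible people are kept for trial reporting and gives as examples "documenting numbers screening, eligible vs. ineligible, and reasons". Earlier involvement is not among those examples.

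**The concern.** The app was built on feedback from the first two phases, and people from those phases may now rate it. Someone who helped shape a product may like it more, use it more, or stay in the study longer than a newcomer. Because the results are meant to inform a larger trial, a planner would want to know whether such people are few or many. If they were many and more favourable, acceptability, usage and 6-week retention could look better than a sample of newcomers would give. Since Section 17 promises no count, a reader of the eventual report might be unable to judge this.

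**Working it through.** **Is the omission real?** Yes. Neither Section 17, the flow-reporting examples in Section 8 nor the assessment battery in Section 9 commits to a count of enrollees from earlier phases.

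**Does it conflict with anything?** No.
- The criteria in Section 6 ask for adults with prenatal alcohol exposure or an FASD diagnosis, English fluency and a smartphone. They do not ask for newcomers, so re-invited people are in the target population.
- Section 7 reaches people who were screened for an earlier phase. Some may never have joined a focus group or answered the survey.
- The Preface describes development work and feedback on a concept, not use of a working app. In Section 9 the baseline surveys come before installation instructions, so the pre-post contrast starts at the same point for everyone.
- The reporting items in Section 8 are introduced as examples. The Screening Form is cited but not reproduced, and the battery lists basic demographics without their content. Earlier involvement may already be collected.
- The team must hold contact details for earlier contacts in order to email them, and it collects contact details again at screening. A later match therefore looks possible. This is my inference; the text does not plan it.

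**How far could the count move retention?** Inputs: 48 enrolled and 40 complete (Section 5, a target), hence 8 not complete. Pooled completion is 40/48 = 83.3%. Let r be the number who took part earlier. The documents do not give r; I take 0 to 24. Between max(0, r − 8) and min(r, 40) of them complete, so completion among the other 48 − r lies between (40 − min(r, 40))/(48 − r) and (40 − max(0, r − 8))/(48 − r).

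| r (assumed) | lower limit | upper limit | most it can be below 83.3% |
|---|---|---|---|
| 0 | 40/48 = 83.3% | 83.3% | 0 points |
| 2 | 38/46 = 82.6% | 40/46 = 87.0% | 0.7 points |
| 5 | 35/43 = 81.4% | 40/43 = 93.0% | 1.9 points |
| 12 | 28/36 = 77.8% | 36/36 = 100% | 5.6 points |
| 24 | 16/24 = 66.7% | 24/24 = 100% | 16.7 points |

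The arithmetic is right, but it says nothing about earlier involvement in particular. Put any other yes/no trait in its place and the table is identical. Each lower limit requires every earlier participant to complete and all 8 losses to fall on the others.

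**Scale against sampling error.** The 95% Wilson interval for 40/48 has centre (0.8333 + 1.96²/96)/(1 + 1.96²/48) = 0.809 and half-width 1.96 × √(0.8333 × 0.1667/48 + 1.96²/(4 × 48²))/(1 + 1.96²/48) = 0.104, giving 70.4% to 91.3%. Its lower end is 12.9 points below 83.3%. The downward limits at r = 2, 5 and 12 are well inside that; the one at r = 24 is not. The upper limits pass 91.3% from r = 5, but in that direction the pooled figure would understate retention among newcomers, the opposite of the worry.

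**Scale for a mean score.** If a share f of the sample differs from the rest by D standard deviations, the pooled mean moves by f × D from the newcomers' mean. With f from 10% to 50% and D from 0.2 to 0.5 SD, all assumed, the shift runs from 0.10 × 0.2 = 0.02 SD to 0.50 × 0.5 = 0.25 SD. The 95% half-width of a mean at n = 40 is t(0.975, 39)/√40 = 0.320 SD, larger than every shift in that range.

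**The case for a change.** The best argument for raising the point is that it is true, relevant to the stated aim and nearly free to meet. One coded variable and one line of counts would tell a planner whether returning contributors were few or many. The qualitative plan already allows themes to be compared across demographics and usage, and a hand in developing the app seems no less relevant to acceptability. The limits above also show that a small count would by itself nearly settle the downward question for retention.

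What stands is that the count would be a useful line in the report. It does not follow that the plan is deficient without it. Section 17 names no participant-level count at all: not country, guardianship, diagnosis against exposure history, or recruitment channel. Other channels in Section 7, such as the partners' own networks and the team's newsletter, could equally bring in engaged people. Singling out one unlisted trait is a choice.

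Going further, to a display without earlier participants, would settle little. The 95% half-width for a mean rises from 0.320 SD at n = 40 to 0.373 SD at n = 30 (17% wider) or 0.468 SD at n = 20 (46% wider), too coarse to establish or exclude a difference. Any trigger for such a display would be arbitrary: the limit at r = 5 is 1.9 points, less than one participant of 48 (1/48 = 2.1 points).

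**Conclusion.** The concern does not hold. The plan is silent on this count, but nothing in it is contradictory, miscalculated or made invalid by the silence. Followed as written, it gives the same pooled descriptives, retention and Cohen's d, and those would remain the main results with the count added. The demonstrated effect is nil. The possible effect is of unknown direction and may be zero: at most 1.9 points downward on retention with 5 earlier participants and 5.6 with 12, reaching 16.7 only if half the sample were earlier participants and every loss fell on the others. These figures rest on the 40-of-48 target, which Section 5 allows to change if attrition is higher, and on assumed values of r. Earlier involvement may already be recorded on forms that the document cites but does not reproduce. What remains is a reporting preference that alters neither what the study does nor what it can conclude.
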